Subjects will perform the tracking test separately for each hand in a block fMRI design. They will perform 9 blocks of two repeating, alternating conditions, Rest and Tracking, each lasting 45 sec for a total of 6 min 45 sec. For all conditions, the sinewave target will be displayed along with the corresponding prompt, "Rest" or "Track," at the bottom of the screen. For each Track condition the subject will attempt to trace the target with the cursor; for each Rest condition they will watch the screen but execute no finger movements. Investigators will visually monitor for extraneous movements, and any subtle mirror movements in the opposite hand will be detected with sensors. Tracking error will be quantified as the average vertical distance of the cursor from the sinusoidal

target during the Track blocks. Prior to testing, subjects will be allotted five 1-min practice trials in a mock scanner in order to mitigate extraneous movement and head motion, and ensure that non-specific factors as fatigue, understanding of the task, etc. do not affect the fMRI signal.

A Siemens Trio 3T scanner (Siemens, Germany) at the Cleveland Clinic will be used. High-resolution (1 mm³), *T*₁-weighted, anatomical images with 176 axial slices and a thickness of 1mm and field of view (FOV) = 256 x 256 mm will be acquired to identify appropriate landmarks and serve as a template upon which functional images would be overlaid. An inversion time/echo (TE) time/repetition (TR) time and flip angle of 1900 msec/1.71 msec/900 msec and 8 degrees will be used. Echo Planar Imaging (EPI) BOLD imaging will be acquired with 160 repetitions of 31-4-mm thick axial slices. Imaging parameters will consist of TE= 29ms, TR= 2.8s, flip angle= 80°, matrix = 128 X 128 and field of view = 256 x 256 mm² providing an in-plane resolution of 2 x 2 mm².

fMRI Metrics

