Activation will be examined in motor cortices bilaterally: primary motor cortex (M1), premotor cortex (PMC), and supplementary motor area (SMA), and in other areas, all of which will be outlined using a standard AFNI atlas as in our previous studies to reduce subjectivity that arises from manually drawing regions around the area of the infarct. For each region, active voxels represent the raw volume of activation or "voxel count". The likelihood of cortical lesions affecting our analysis will be reduced by excluding false positive activation found in infarcted regions. The following indices will be derived to quantify functional re-mapping.

Laterality Index: Since our previous work and that of others have found that activation shifts to predominantly ipsilesional motor cortices with significant gains in dexterity, we will study whether the balance of activation between ipsi- vs. contralateral M1, S1 and PMC shifts to the ipsilesional hemisphere with greater recovery.¹⁸⁻²¹ Voxel counts will be normalized by comparing *between* the two hemispheres using a laterality index that is calculated as follows.^{18,19,22,23} Laterality index = (I - C) / (I + C), where I = the active voxel count in the ipsilesional hemisphere and C = the active voxel count in the contralateral hemisphere. The range of possible values is -1 (entirely contralateral activation) to +1 (entirely ipsilesional activation). Laterality of brain activity during movement of both the paretic

and non-paretic hands will be studied, providing a strong within-subject control. Although the brain activation during non-paretic hand movement cannot be considered "normal", it offers a reasonable method of normalizing and investigating recovery within and across subjects.

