- Electrical stimulation should not be used by patients with implanted electronic devices (cardiac demand pacemakers etc.) unless under specialized medical supervision.
- Do not participate in this study if you have a history of potentially fatal cardiac arrhythmias.
- Electrical stimulation should not be used by people who have poorly controlled epilepsy.
- The stimulator has been programmed specifically for the intended user only. Do not let others use the stimulator.

Statistical Analysis Plan

We hypothesize that the CCFES+HTVG group will have greater post-treatment gains than the CCFES group on upper extremity motor outcomes. Exploratory looks at the data will be done before fitting our models. The adaptive randomization should force relatively good balance of potential confounding variables (e.g., fMRI eligible, severity of impairment, time post-stroke), but imbalances in treatment adherence or any other baseline covariate (e.g., lesion location, etc.) or adherence may still require their inclusion as covariates. Each measure will be modeled using a linear mixed effects approach which is well-suited for handling correlated repeated measurements, unbalanced data, and missing data and dropouts in longitudinal studies, while permitting us to control for potential confounders.¹ Least square (LS) means will be calculated using model estimates and adjusted for missing values for each group at each time point. This approach allows comparisons and estimates of treatment group effects at any time point, and also allows comparisons and estimates across time points within groups to evaluate the persistence or decay of the treatment effect. Secondarily, we hypothesized that participants who were less than 2 years after stroke or had moderate hand impairment at baseline would improve more than participants who were more than 2 years after stroke or had severe hand impairment at baseline. A mixed effects modeling analysis will be used similar to the primary analysis to evaluate the effects of time post-stroke and impairment severity. For fMRI data, differences from baseline to EOT in beta coefficient maps for each region of interest will be evaluated with paired t-tests and cluster threshold set to >100 voxels. Between-group comparisons will be made with independent t-tests.

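### The fixed 100-voxel cluster rule for the exploratory fMRI maps is not tied to a voxel-level p value, map smoothness or counting grid, so its false-positive rate is uncontrolled

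*Combined protocol and SAP*

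**What the plan says.** The whole inference rule for the fMRI maps is two sentences at the end of the Statistical Analysis Plan. The first says that "differences from baseline to EOT in beta coefficient maps for each region of interest will be evaluated with paired t-tests", with "cluster threshold set to >100 voxels". The second says "Between-group comparisons will be made with independent t-tests" and gives no cluster rule, alpha or correction.

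The section on fMRI procedure and equipment gives the acquisition: "160 repetitions of 31-4-mm thick axial slices", "providing an in-plane resolution of 2 x 2 mm²". It also describes a 1 mm³ anatomical image to "serve as a template upon which functional images would be overlaid". It does not say on which grid the 100 voxels are counted.

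The fMRI Metrics section names primary motor, premotor and supplementary motor cortex on both sides, "and in other areas, all of which will be outlined using a standard AFNI atlas", and then lists further parietal, prefrontal, cingulate, striatal and cerebellar regions. It refers to active voxels and to voxel t-statistics but gives no cut-off for either. No smoothing kernel, estimated smoothness, connectivity rule or target error rate appears anywhere.

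Specific Aims presents Aim 3 as exploratory, and General Study Design makes the scans optional.

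**The concern.** A cluster-extent threshold has no false-positive rate of its own. How large noise clusters grow depends on the voxel-level cut-off that forms them, the smoothness of the map, the voxel size and the volume searched. The plan fixes the extent and leaves most of the rest open. The same 100-voxel rule can then pass noise clusters under a lenient voxel p over a large search volume, or demand far more than a 5% rule needs under a strict one.

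At stake are the within-group maps of activation change that feed Aim 3. If the voxel p, smoothing and grid are chosen after the data are seen, the same scans could show several clusters of change or none, and a reader could not attach an error rate to either result.

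**Working it through.** The plan states no error rate for the maps, so there is no figure of its own to reproduce. The check has two parts.

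**1. What 100 voxels means physically**

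- Acquired voxel: 2 x 2 x 4 mm = 16 mm³. So 100 voxels = 1,600 mm³ = 1.6 mL.
- If the voxels were counted on a 1 mm³ grid: 100 voxels = 100 mm³ = 0.1 mL, a 16-fold difference. The documents do not say that this grid is used.
- On the acquired grid, an assumed 20 cc region holds 20,000 / 16 = 1,250 voxels, so a cluster must fill 8% of it. An assumed 8 cc region holds 500 voxels, so a cluster must fill 20%.

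**2. False-positive rate under the null**

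The quantity is the probability of at least one cluster of more than 100 voxels in pure noise. Gaussian noise was smoothed to a given full width at half maximum (FWHM) and thresholded two-sided. Clusters were formed by face connectivity, with positive and negative clusters kept separate. From the documents: the 100-voxel extent, the acquired voxel size and testing by region. Assumed: voxel p, FWHM and search volume.

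Acquired grid, voxel p<0.05:

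| Search volume | 4 mm | 6 mm | 8 mm | 10 mm | 12 mm |
|---|---|---|---|---|---|
| One 20 cc region | 0% | 0.2% | 1.5% | 8.8% | 13% |
| One 100 cc region | – | 0.2% | 18% | 44% | 62% |
| About 500 cc combined | – | 8% | 73% | 98% | – |
| Whole brain (1,495 cc) | 0% | 20.5% | 99% | 100% | 100% |

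(A dash means that no figure is given.) The 20 cc and 100 cc cells at 6–12 mm use 600 runs each. The Monte Carlo standard error of the 62% cell is √(0.62 x 0.38 / 600) = 2 percentage points. A whole-brain check with t-maps on 19 degrees of freedom (an assumed subset size, 40 runs per setting) gives 0%, 10%, 95% and 100% at 4, 6, 8 and 10 mm.

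Error also adds up over regions. For six regions (the three named motor areas on both sides), each taken as 20 cc and independent, at 10 mm: 1 − (1 − 0.088)⁶ = 42%. This is an illustration only, since neighbouring regions are correlated.

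At stricter voxel cut-offs on the acquired grid:

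- p<0.01: at most 0.8% for 20 cc and 8% for 100 cc. Whole brain is 0%, 0%, 2%, 28% and 65.5% at 4, 6, 8, 10 and 12 mm.
- p<0.001: 0% in almost every setting, at most 1% (whole brain, 12 mm).

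**Extent that would hold 5% at p<0.001, acquired grid**

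- One 20 cc region: 3, 4, 7, 9 and 10 voxels at 4, 6, 8, 10 and 12 mm.
- Whole brain: 6, 16, 32, 51 and 76 voxels.
- Regional search volumes at moderate smoothness: about 4 to 40 voxels. The fixed rule is then 100 / 40 = 2.5 to 100 / 4 = 25 times larger than needed.

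Some settings do put 100 close to a 5% threshold. On the acquired grid these include one 20 cc region at p<0.05 and 10 mm (107 voxels) and whole brain at p<0.01 and 8 mm (91 voxels). The plan does not select them.

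**Sensitivity to the grid.** For one 20 cc region counted at 1 mm³, the rate is 91–100% at p<0.05 and 0–5% at p<0.001 (4–8 mm).

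**The case against.** The strongest reply is that the plan tests by region, not over the whole brain, in an aim that is openly exploratory and optional, and that it claims no family-wise control. All of this stands. For one small region on the acquired grid the rate at p<0.05 is 0–13%, which is not alarming, and nothing in the documents presents the 100-voxel rule as a corrected threshold. Against it, the list of regions is open-ended, there are two hands and two sets of scans, and no correction across them is stated. The combined search can therefore be large.

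Several stronger readings are tempting and are not supported:

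- That this trial's false-positive rate lies anywhere from 0% to 100%. The top of that range needs a whole-brain search or a finer grid, together with a lenient voxel p. The range describes what the wording leaves open; it does not estimate this trial's error.
- That voxels are counted at 1 mm³. The anatomical image is described as an overlay template, which may concern only localisation and display. The acquired voxel size is given; only the counting grid is missing.
- That Hypothesis 3 depends on which clusters survive. It compares the two groups, whereas the rule is attached to the within-group paired tests. The laterality index and the volume and intensity measures are separate outcomes.
- That real change in small regions will be lost. The strictness at p<0.001 is shown, but the documents give no region volumes or effect sizes from which to compute power.

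**Conclusion.** The point holds in conditional form. The 100-voxel rule has no stated link to a voxel-level cut-off, smoothness or counting grid, so its false-positive rate is uncontrolled. At an assumed p<0.05 on the acquired grid, the rate depends mainly on how much tissue is searched and how smooth the maps are. It is modest for one small region and high for large or combined volumes at 8 mm or more. At p<0.001 false clusters are rare on that grid, and the rule is instead several times too strict for a 5% target.

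These sizes rest on assumed voxel p, smoothness and region volumes, and on Gaussian noise. The conclusion that 100 voxels is uncalibrated does not depend on any one of these choices. It concerns the activation maps of Aim 3 only. The primary Box and Blocks analysis is untouched.

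**What to change.** Replace the fixed 100-voxel extent in the Statistical Analysis Plan with a calibrated rule, written down before the maps are analysed:

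- State a cluster-forming voxel p and its sidedness, for example two-sided p<0.001, and the connectivity rule.
- State the analysis grid, and name in advance one mask that combines all regions to be searched.
- Derive the extent by simulation from the estimated residual smoothness, on that grid and within that mask, to give 5% family-wise error. Another pre-specified correction with the same target would also serve.
- Apply the same rule to the between-group maps, and say how the two hands and the two scan sets are handled.
- Label any map that still uses the 100-voxel rule as exploratory and uncorrected.

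The cost is a change of wording and a little analysis work, with no new data or visits. The protocol names an AFNI atlas but does not commit to a software package for inference, so the tool should be stated as well. The downside is that some clusters that pass a lax rule would no longer be reported.

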Clinical Significance: This study will demonstrate the supplemental motor relearning value of virtual reality/video games to CCFES therapy, (2) identify patients most likely to respond to both therapies, and (3) determine whether adding HTVG to CCFES simply enhances cortical activation underlying CCFES or engages additional cortical areas to improve response across broader ranges of severity and chronicity. This study is an important step toward the development and dissemination of new

treatments that may be applicable and effective across a wide range of patients who have lost hand function after stroke.

Specific Aims

AIM 1: Determine the effect of integrating Hand Therapy Video Games (HTVG) with Contralaterally Controlled Functional Electrical Stimulation (CCFES) on upper extremity motor outcomes

Hypothesis 1: Stroke patients treated with CCFES+HTVG will have greater and faster improvements in hand dexterity, upper limb impairment, and activity limitation than those treated with CCFES alone

AIM 2: Evaluate the effect of baseline impairment and time post-stroke on treatment response

Hypothesis 2: Compared to CCFES, CCFES+HTVG will benefit patients with greater baseline impairment and time elapsed post-stroke.

AIM 3: Explore the effects of CCFES+HTVG vs. CCFES on cortical activation during a hand task

Hypothesis 3: Compared to CCFES, CCFES+HTVG will exhibit greater re-mapping in the brain, demonstrated as greater lateralization of activity, greater recruitment of learning- based networks in ipsilesional and contralesional regions, and increased intensity of cortical activity.

Methods and Procedures

General Study Design

A single-blinded randomized controlled trial will be carried out to assess the effects of 12 weeks of CCFES+HTVG compared to CCFES. Dexterity, upper limb impairment, and activity limitation will be assessed at 0 (baseline), 3, 6, 9, 12 (end of treatment), 24, and 36 wks. Cortical activation (measured with fMRI) will be optionally assessed at 0 and 12 wks. The treatment dose will be the same for both groups: 10 sessions per week (7.5 hrs) of self-administered treatment at home plus 2 sessions per week (3 hrs) of group-specific occupational therapy in the lab.

Device

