Stimulation is delivered through standard self-adhering pre-gelled 2"x2" square and 1.25" round electrodes (e.g., PALS®, Axelgaard Manufacturing, Fallbrook, CA). The analog input source for the stimulator is an assembly of three passive bend sensors 1/4" wide by 4 1/2 " long (Spectra Symbol, Salt

Lake City, UT) which are either attached by Velcro or inserted through slits cut into the top of the index, middle, and ring fingers of an athletic glove.³ The sensors act as variable resistors. When the fingers open and close, the electrical impedance of each sensors changes; these impedance changes are supplied as the analog input to the stimulator. The stimulator is programmed to produce current pulses with pulse widths (intensities) that are proportional to input from the glove worn on the nonparetic hand.

The CCFES+HTVG system uses a bend sensor that is worn on a finger of the paretic hand to detect opening and closing. The sensor is attached to a fingerless “glove” and plugs into an analog-to-digital converter module, which in turn plugs into a USB port on a 17-inch touchscreen laptop computer. The computer is an all-in-one unit that requires no other components besides the monitor’s touchscreen (no keyboard or mouse) to select and play the games. The computer is configured so that it can only be used for the game play prescribed to the participant and requires a USB key from the investigators to run.

Randomization

Subjects will be assigned to a treatment group using an adaptive randomization algorithm⁵ to minimize group imbalances on 4 key patient characteristics: (1) time post-stroke (< 2 yrs vs. \geq 2 yrs), (2) baseline motor status (moderate vs. severe), (3) paretic side (dominant vs. non-dominant),⁶ and (4) fMRI eligibility (yes vs. no). Patients with $\geq 10^\circ$ active wrist extension, 10° active thumb abduction/extension, and 10° active extension in at least two additional digits will be considered to have “moderate” impairment, and patients with less movement than that who meet all the other motor criteria (see Section 30) will be considered to have “severe” impairment.⁷

Device Set Up

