Volume and Intensity of Activation: Regions in parietal associative, prefrontal and cingulate motor cortices, striatum, and cerebellum may become activated over the course of learning with CCFES+HVTG. Therefore, based on our work and others in fMRI,^{20,24,25} we will record volume and intensity of activation of these areas at pre- and post-treatment. The volume, center of mass (avg x, y, z Talairach coordinates),^{26,27} and change in BOLD signal intensity (contrast estimate or % increase in β in GLM)^{18,28-30} for these regions will be studied. BOLD signal intensity indicates the level of activation of neural networks during performance of a task.³¹ We will also identify voxels active at both pre- and post-treatment and note whether intensity increases. Each voxel has a t-statistic value reflecting its difference in intensity from "Rest" to "Track". The average t-statistic value of all voxels in a common cluster will be compared from pre- to post-treatment.³²

Audio/Visual Recordings

Subjects will be video recorded during the motor outcome assessments to capture a visual documentation of treatment effects. Subjects may be video recorded during the treatment sessions to demonstrate the treatment and outcomes and for scientific and educational presentation purposes.

Selection Criteria

Inclusion criteria:

- > 6 months since a first clinical cortical or subcortical (but not brainstem), hemorrhagic or nonhemorrhagic stroke
- age 21-80 years old
- unilateral upper limb hemiparesis with finger extensor strength of \leq grade 4/5 on the MRC scale AND a score of ≥ 1 and $\leq 11/14$ on the hand section of the upper extremity Fugl-Meyer Assessment

- adequate active movement of the shoulder and elbow to position the hand in the workspace for table-top task practice (necessary for the lab task practice sessions)
- able to follow 3-stage commands
- able to remember 2 of 3 items after 30 minutes
- surface stimulation of the paretic finger and thumb extensors produces functional hand opening without pain (this will exclude those who have degree of flexor hypertonia that prevents stimulated hand opening)
- Functional passive range of motion (minimal resistance) at elbow, wrist, fingers, and thumb (i.e., there exists enough PROM to reach and acquire table-top objects).
- intact vision and hearing
- medically stable
- full voluntary opening/closing of the contralateral (less affected) hand

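### The between-arm fMRI comparison is a valid but unadjusted t-test; adjusting for the baseline scan, and where numbers allow the minimisation factors, would be more precise

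*Combined protocol and SAP*

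**What the plan says.** The last two sentences of the Statistical Analysis Plan cover fMRI. The first says that "differences from baseline to EOT in beta coefficient maps for each region of interest will be evaluated with paired t-tests", with a cluster-size threshold. The second says "Between-group comparisons will be made with independent t-tests". The second sentence names neither its dependent variable nor any covariate.

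Other parts of the document bear on this:

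- **Baseline scan.** General Study Design: "Cortical activation (measured with fMRI) will be optionally assessed at 0 and 12 wks". Under fMRI Metrics, for the further regions of interest, "we will record volume and intensity of activation of these areas at pre- and post-treatment". The same section defines a laterality index running from -1 to +1.
- **Allocation.** Randomization uses an "adaptive randomization algorithm⁵ to minimize group imbalances on 4 key patient characteristics": time post-stroke, motor status, paretic side and fMRI eligibility.
- **Covariates.** The SAP allows for covariates if adherence or baseline variables turn out unbalanced, and it describes control for confounders as a feature of the mixed model. Neither statement is carried over to the fMRI t-tests.
- **Status and size.** Aim 3 is exploratory. Up to 52 participants are to be randomised. The number to be scanned is not stated.

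**The concern.** Hypothesis 3 is a between-arm claim, so the independent t-test is the analysis that answers Aim 3. It is applied to what is probably the smallest data set in the trial, since scanning is optional and some participants will be ineligible. Two pieces of information already in hand are left out of the model.

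The first is the baseline value as a covariate. Subtracting baseline fixes its coefficient at 1. When the true slope is below 1, a chance difference between arms at baseline is over-corrected. With equal variances at the two scans, the change-score estimate moves by -(1-r) for each unit of baseline difference. The bounded laterality index is an obvious case: a participant already near +1 has little room to shift further.

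The second is the set of factors used to balance the arms. The SAP itself expects time post-stroke and severity to predict motor improvement, and the fMRI Metrics section links shifts in activation to gains in dexterity. The fMRI procedure also scales the tracking task differently for participants with less than 10° of finger movement, so severity can alter the scanner task. It is plausible, though not shown, that these factors predict change in activation.

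At stake are the width of the confidence interval for the arm difference and the chance of detecting a difference. The validity of the test is not at stake.

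**Working it through.** The documents give no power, alpha, SD, effect size, baseline–EOT correlation or number scanned for fMRI, so there is no figure of the plan to reproduce. Everything below marked as assumed is shown over a range.

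**1. Baseline adjustment, large-sample variance.** Assume equal variance s² at the two scans and correlation r. The variance per participant entering the arm difference is:

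- EOT value only: s²
- Change score: 2(1-r)s²
- Baseline-adjusted (ANCOVA): (1-r²)s²

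Hence ANCOVA / change score = (1-r²) / [2(1-r)] = (1+r)/2, and ANCOVA / EOT only = 1-r².

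| assumed r | ANCOVA / change | SE ratio (square root) | ANCOVA / EOT only |
|---|---|---|---|
| 0.3 | 0.65 | 0.81 | 0.91 |
| 0.5 | 0.75 | 0.87 | 0.75 |
| 0.7 | 0.85 | 0.92 | 0.51 |
| 0.9 | 0.95 | 0.97 | 0.19 |

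**2. Small-sample cost of estimating the slope.** With N scanned and k chance-balanced covariates, the variance rises by about (N-3)/(N-3-k). For an assumed 15 per arm (N = 30) and k = 1 this is 27/26 = 1.04. The ratios to the change score become 0.65 × 1.04 = 0.68, then 0.78, 0.88 and 0.99. The gain is used up when (1+r)/2 × 27/26 = 1, that is at r = 52/27 - 1 = 0.93.

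**3. What this means for power.** Assumed: 15 per arm, a true difference of 0.8 SD, two-sided 5%, normal approximation, power = Φ(0.8 / √(2v/15) - 1.96), with v the variance factor from step 1.

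| assumed r | change score | EOT only | ANCOVA | ANCOVA with the 27/26 cost |
|---|---|---|---|---|
| 0.3 | 46% | 59% | 63% | 62% |
| 0.5 | 59% | 59% | 72% | 70% |
| 0.7 | 81% | 59% | 87% | 85% |

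**4. Minimisation factors.** Simulation with 4000 runs per setting: N = 52, four binary factors, an assumed 0.8 biased coin, no treatment effect, and a two-sided 5% test on change scores. Three factors (motor status, time post-stroke, paretic side) together explain an assumed share R² of the variance in change. fMRI eligibility is constant among those scanned.

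| scanned | R² | unadjusted type I error | model SE / empirical SE | type I error, adjusted for 3 factors |
|---|---|---|---|---|
| all | 0 | 5.0% | 0.276 / 0.277 | 5.0% |
| all | 10% | 3.9% | 0.276 / 0.267 | 5.0% |
| all | 20% | 3.1% | 0.276 / 0.250 | 5.1% |
| all | 40% | 1.2% | 0.277 / 0.224 | 4.4% |
| about 60% | 0 | 5.7% | 0.356 / 0.371 | 5.0% |
| about 60% | 10% | 4.7% | 0.356 / 0.354 | 5.7% |
| about 60% | 20% | 4.0% | 0.358 / 0.350 | 6.0% |
| about 60% | 40% | 2.7% | 0.360 / 0.315 | 3.9% |

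At R² = 40% the unadjusted SE is too wide by 0.277/0.224 - 1 = 24% with all scanned, and by 0.360/0.315 - 1 = 14% with about 60% scanned. At R² = 0 the factors create no mismatch; with 4000 runs, simulation error on a 5% rate is about √(0.05 × 0.95 / 4000) = 0.3 percentage points. The price of adjusting for three useless factors with about 60% scanned is a mean SE of 0.366 against 0.356, about 3%.

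**The case against.** A reader might infer that the test ignores the baseline scan. The documents do not support that. The sentence before it defines the fMRI quantity as the baseline-to-EOT difference, so on the natural reading baseline is subtracted. An EOT-only comparison is not excluded, because the input is not stated, but it is the less likely reading.

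A reader might also infer that the error bars are wrong in a way that produces false positives. They are not. A mismatch arises only if the minimisation factors predict change in activation, on which the documents give no evidence, and it then runs in the conservative direction. It is smaller in a scanned subset, where balance is forced only indirectly.

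It would likewise be too strong to call adjustment free, or never worse. The ratio (1+r)/2 assumes equal variances and a large sample. With an assumed 20 scanned and three chance-balanced covariates, two of them uninformative, the cost factor is 17/14 = 1.21, and at r = 0.7 the ratio becomes 0.85 × 1.21 = 1.03, so the gain is gone. This stands as a caution about how many covariates to add. Baseline alone costs little.

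Finally, Aim 3 is exploratory, scanning is optional, and a change-score t-test is a valid comparison under randomisation. All of this stands, and it limits the severity. It gives no reason to prefer the less precise method.

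**Conclusion.** The point holds as a matter of precision and specification. The plan names an unadjusted test, leaves its dependent variable unstated, and does not use the baseline value as a covariate.

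Against a change-score test, with an assumed 15 scanned per arm and after the slope cost, baseline adjustment cuts the standard error by about 18%, 12% and 6% at r = 0.3, 0.5 and 0.7 (1 minus the square roots of 0.675, 0.779 and 0.883). It gains almost nothing at r = 0.9. If the test was meant for EOT values alone, the gain runs the other way with r and is large when r is high.

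The part about the minimisation factors is conditional: up to 24% excess width in the standard error in the most favourable assumed case, none if the factors are not prognostic. All of this rests on assumed r, R², biased coin and number scanned. The matter is minor, because the planned test is valid and the aim is exploratory.

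**What to change.** State the dependent variable. For each region-level fMRI summary (beta, laterality index, volume), replace the independent t-test with a linear model of the EOT value on arm and baseline value, and report the adjusted arm difference with its 95% CI.

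Add the minimisation factors that vary among those scanned (motor status, time post-stroke and paretic side) where the number scanned allows. Fix that rule in advance, without reference to the results. fMRI eligibility should be constant in this subset and can be left out.

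Keep the paired, cluster-thresholded map analyses as within-arm description, and say that the between-arm inference comes from the region-level models.

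The cost is a short addition to the SAP and no new data. The statistical cost is a few degrees of freedom: about 4% in variance for baseline with 15 per arm, and about 3% in standard error for three factors that prove not to be prognostic when about 60% are scanned.
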